2.10 Analysis plan

Baseline data will be summarized descriptively. The primary outcome of 90-day mortality will be evaluated using an intent-to-treat approach. A simple comparison of proportions will be performed using a chi-squared test. The risk ratio and relative risk reduction will be estimated with 95% confidence intervals. An adjusted analysis will also be completed using logistic regression and will include the following baseline variables: age, sex, sepsis, receipt of cardiopulmonary bypass and SOFA score.

The principal secondary outcome, the proportion of survivors who are RRT dependent at 90 days, presents challenges as the non-inclusion of participants who died might obviate the inter-group balance afforded by randomization. We will consider two complementary approaches to examine this question. First, we will use the adjusted model for the primary outcome to estimate the probabilities of 90-day survival. We will then use the reciprocals of these as weights in a logistic regression for RRT, resulting in an inverse probability weighted analysis. This is typically called a marginal structural model. The second approach will employ a multinomial regression model to jointly consider the states: dead at 90 days, alive at 90 days receiving RRT and alive at 90 days RRT-free. A similar approach will be used to estimate the probabilities of 365-day survival and to consider the states: dead at 365 days, alive at 365 days receiving RRT and alive at 365 days RRT-free.

Duration of ventilation, vasoactive therapy, ICU stay and hospitalization and albuminuria at 90 days (expressed as the urinary albumin to creatinine ratio in mg/mmol) will be compared by means of a t-test. Finally, eGFR decline of 25%, death in ICU, by 28 days and in-hospital, and ICU readmission and rehospitalization within 90 days will be compared by chi-squared tests.

Interim analyses for efficacy based on the primary outcome will be done when 25, 50 and 75% of planned enrollees have completed 90-day follow-up. Given the risks of false positive results with early stopping for benefit, statistical significance will be declared using small p-values established by O'Brien-Fleming boundaries on the primary outcome (90-day mortality). A detailed monitoring plan will be developed in consultation with the DSMB prior to commencement of recruitment.

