The STARRT-AKI trial population will include a minimum of 2866 patients, in order to have at least 90% power to detect a 15% relative reduction (6% absolute risk reduction) in the risk of death, assuming an estimated baseline 90-day all-cause mortality of 40%. The baseline mortality rate was based on the available published literature and data from our pilot trial.^{14,15} A 15% relative risk reduction required a total sample of 2718 (1359 patients per arm); however, to account for the three planned interim analyses and an estimated combined rate of crossover, dropout and loss to follow-up of 3%, the total sample size was increased to include a minimum of 2866 patients. Following the planned third interim analysis, performed when 75% of recruitment had been achieved (24 April 2019), the Data Safety Monitoring Board (DSMB) supported the extension of recruitment to achieve a sample size of a minimum of 3000 patients.

Statistical analysis

Analysis principles

Analysis will be performed on an intention-to-treat (ITT) basis. ● All tests will be two-sided and the overall type I error probability for the primary outcome will not exceed 5% ($\alpha = 0.05$) over the three interim analyses by employing an O'Brien—Fleming stopping boundary. This approach gives P values thresholds for stopping at each of the interim analyses of 0.00001473, 0.003045 and 0.0183, respectively, and a required significance level of 0.044 at the final analysis.¹⁶ The primary outcome will be analysed independently by two statisticians. For secondary analyses and endpoints, P values will be reported, but since these are best viewed as exploratory, formal hypothesis testing (ie, for rejection of null hypotheses) will be avoided. ● This SAP and the main STARRT-AKI trial manuscript will only include analyses up to 90 days after randomisation. ● The analysis of one-year outcomes (eg, mortality, dialysis dependence, health-related quality of life) and health economic outcomes will be reported separately and the analytic approach to these outcomes will not be covered in this SAP.

- Pre-specified subgroup analyses will be performed irrespective of the result for the primary outcome.
- Secondary outcome analyses will be performed irrespective of the result for the primary outcome and will be considered exploratory.

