- The secondary analyses will not be adjusted for multiple testing; however, the results of all statistical testing will be reported according to the American Statistical Association guidelines to provide the necessary context for interpretation.¹⁷
- All estimates of treatment effect will be accompanied by 95% confidence intervals (CI).
- All analyses will be performed using the R software package (R Core Team, 2008; www.R-project.org).

Interim analyses and the Data Safety Monitoring Board

An independent DSMB will review unblinded data to examine recruitment rate, patient characteristics, randomisation compliance, treatment compliance, completeness of data, outcomes and adverse events on three occasions (following the completion of 90-day follow-up for the 716th, 1432nd and 2150th patient, respectively). The DSMB charter is available at: <https://www.ualberta.ca/critical-care/research/current-research/starrtaki/documents.10>

Analysed datasets

All main analyses will be performed on the ITT population dataset. For these analyses, all patients will be analysed according to the group to which they were randomised; however, any randomised patient found to have not fulfilled eligibility criteria based on data available at the time of initial assessment (ie, randomised in

error) will be excluded following independent adjudication by two investigators who will be blinded to outcomes.¹⁸

Trial profile

The flow of patients through the trial will be shown in a Consolidated Standards of Reporting Trials (CONSORT) diagram (Figure 1).¹⁹ The figure will provide a summary of the number of patients screened, the number of patients who fulfilled eligibility, the number of patients who were excluded and the reason(s) for exclusion.

Patient characteristics and baseline comparisons

- A description of baseline characteristics will be presented by treatment allocation, as outlined in the proposed Table 1 .
- Categorical variables will be summarised with frequencies and percentages. Percentages will be calculated according to the number of patients for whom data are available.

- Continuous variables will be summarised as means with standard deviation (SD) or medians with the interquartile range (IQR) (Q1 and Q3).

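### The SAP places the third interim look at 75% of recruitment, elsewhere at 75% with completed 90-day follow-up; the fixed final level of 0.044 should be recomputed at the actual information fractions

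*SAP*

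**What the plan says.** Two places define when the efficacy looks happen, and they agree. Protocol 2.10 says the looks "will be done when 25, 50 and 75% of planned enrollees have completed 90-day follow-up". The SAP section on interim analyses and the DSMB gives the same rule in patient numbers: "following the completion of 90-day follow-up for the 716th, 1432nd and 2150th patient, respectively". The third number fits, since 0.75 x 2,866 = 2,149.5.

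A third place describes the last of these looks as already done. The SAP's Sample size section reads "Following the planned third interim analysis, performed when 75% of recruitment had been achieved (24 April 2019", and continues that the DSMB supported extending recruitment to at least 3,000. It does not mention follow-up.

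Under Analysis principles the SAP caps overall two-sided type I error for the primary outcome at 5%. It gives "thresholds for stopping at each of the interim analyses of 0.00001473, 0.003045 and 0.0183, respectively", and "a required significance level of 0.044 at the final analysis".

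**The concern.** The primary outcome is death by 90 days, so a patient recruited less than 90 days before a look and still alive has no outcome at that look. A look at 75% of recruitment therefore holds less than 75% of the information.

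The stopping thresholds depend on that fraction. If the third look came earlier than planned, 0.0183 was too lenient for it, and keeping 0.044 at the end takes the total above 5%. Neither document reports how many patients had a known 90-day outcome at any look, so a reader cannot confirm the 5% cap or the level at which the primary result will be judged.

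**Working it through.** **1. Can both descriptions be literally true?** The SAP is dated 23 May 2019 and reports the look as done.
- If 75% of recruitment was reached on 24 April 2019, the 2150th patient could not complete 90 days before 23 July 2019, two months after the SAP's date.
- If the look on 24 April 2019 followed completed follow-up of the 2150th patient, that patient was enrolled by about 24 January 2019. Unless enrolment then paused, recruitment had passed 75% by the date of the look.

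So the Sample size sentence and the interim-analysis section cannot both be exact.

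**2. Reproducing the SAP's thresholds.** Inputs: two-sided alpha 0.05 and looks at t = 0.25, 0.50, 0.75 and 1. The O'Brien-Fleming-type spending function is A(t) = 4[1 - Φ(z/√t)], with z = Φ⁻¹(1 - 0.05/4) = 2.2414. Cumulative alpha spent is 0.0000147, 0.00305, 0.01930 and 0.0500. Solving for the boundaries by recursive numerical integration, with correlation √(ti/tj) between looks, gives nominal p-values of 0.00001473, 0.003045, 0.01832 and 0.04400. All four match the SAP. Classic O'Brien-Fleming would give 0.0000515, 0.0042, 0.0194 and 0.0429, which do not match. The stated thresholds therefore belong to exactly 25/50/75/100% information, where overall error is 5.00%.

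**3. How many patients might have been pending?** This is an assumption, because the documents give no count. Patients enrolled in 90 days = monthly rate x 90/30.44.
- Low: 2,150 patients between the protocol date given in the SAP (5 October 2015) and 24 April 2019, about 42.6 months, is about 50 per month, or about 150 pending.
- Middle: 2,866 in the 3 years of protocol 2.11 is 79.6 per month, or about 236 pending.
- High: the SAP's estimated 170 sites at 1 per site per month (the lower rate in protocol 2.11) is 170 per month, or about 500 pending.

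**4. Overall error if the sentence is literal.** Final N = 2,866, only completers analysed, looks 1 and 2 as planned, stated thresholds kept:

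| Completers at look 3 | Fraction | Spending threshold at look 3 | Overall error with 0.0183 and 0.044 | Final level that keeps 5% |
|---|---|---|---|---|
| 2,150 (as planned) | 0.750 | 0.0183 | 5.00% | 0.0440 |
| 2,000 | 0.698 | 0.0136 | 5.10% | 0.0429 |
| 1,914 | 0.668 | 0.0112 | 5.15% | 0.0423 |
| 1,650 | 0.576 | 0.0054 | 5.30% | 0.0406 |

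The last column takes 0.0183 as already used.

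**5. The same with the planned extension.** At a final N of 3,000 the first two fractions become 716/3,000 = 0.239 and 1,432/3,000 = 0.477. Power is for 40% v 34% with no dilution from crossover or dropout.

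| Completers at look 3 | Fraction | Overall error with 0.044 | Final level that keeps 5% | Power, 0.044 → corrected level |
|---|---|---|---|---|
| 2,150 | 0.717 | 5.07% | 0.04315 | 92.2% → 92.1% |
| 1,914 | 0.638 | 5.21% | 0.04159 | 92.3% → 91.9% |
| 1,650 | 0.550 | 5.35% | 0.0401 | 92.3% → 91.7% |

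**The case against.** The strongest reply is that the Sample size sentence defines nothing. It is a past-tense aside explaining the extension, and it calls the look the planned one, which points back to the rule in protocol 2.10 and the SAP's interim-analysis section. On that reading 2,150 completers were analysed and, for 2,866 patients, every stated number is exact. The documents do not say whether 24 April 2019 is a recruitment milestone, a data cut or a DSMB meeting. The DSMB charter and monitoring plan, which might settle it, are not part of these documents. Patients who had already died by the look had a known outcome, so the number pending is also uncertain. Finally, the excess is a few tenths of a percentage point, and the trial was not stopped at the look.

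Most of this stands. A reader might infer that the third look was certainly early and the 5% cap has been broken; the documents do not support that, because loose wording remains an open reading. A reader might also infer that all three looks were run by recruitment. Nothing supports that either, since only the third is described that way.

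Two things survive. The sentence is the only account of what was done, and the SAP's dates rule out taking it and the stated trigger both at face value. And loose wording does not rescue 0.044 once the final number is at least 3,000: with exactly 2,150 completers it gives 5.07%.

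**Conclusion.** The descriptions of the third look conflict and need reconciling. Whether type I error is affected by the look's timing depends on a count that the documents do not give. For a final N of 2,866 the error is 5.00% if 2,150 completers were analysed. It is about 5.1-5.3% if the look was at 75% of recruitment with 150-500 patients pending and only completers analysed. For a final N of 3,000 the corresponding figures are 5.07% and, for 1,914 completers, 5.21%.

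The size is modest: 0.1-0.3 percentage points at 2,866, and slightly more at the far end of the assumed range at 3,000. In practice it matters only if the final p-value falls between about 0.040 and 0.044. It is still worth settling, because 0.044 is the stated decision threshold for the primary outcome and the correction is cheap.

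The calculations assume that information is proportional to the number of patients with a 90-day outcome, that looks 1 and 2 took place as planned, and that the final number was not chosen from the unblinded treatment comparison.

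**What to change.** 1. Reword the Sample size sentence so that it agrees with protocol 2.10 and the SAP's interim-analysis section, or state plainly that the look was held at a different point. Say what 24 April 2019 refers to.
2. Report how many patients had a known 90-day outcome at the third look, and preferably at all three.
3. Before database lock, replace the fixed 0.044 with a rule: the final level comes from the same spending approach at the actual information fractions, given the thresholds already used and the actual final number of patients. As illustrations at 3,000 patients, this gives 0.04315 with 2,150 completers at look 3 and 0.04159 with 1,914.

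The cost is one corrected sentence, the counts and one boundary calculation. At 3,000 patients the power lost under the design assumptions is about 0.1 point with 2,150 completers, 0.3 with 1,914 and 0.5 with 1,650.

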2.9 Sample size justification

We expect a 90-day mortality of 40% in the standard arm. This mortality rate is compatible with 90-day mortality reported in contemporary cohorts of patients with RRT-requiring AKI in Finland and Australia/New Zealand.^{4,21} There is no clear guidance on the estimated risk reduction afforded by accelerated RRT so we have selected a relative risk reduction of 15% (absolute risk reduction 6%) as recommended by experts to be an effect magnitude that is minimally important and conceivable with this intervention.⁴⁹ With Type I error of 0.05 and power of 0.90, a sample size of 1,359 patients/arm would be required (total 2,718). In order to account for the interim analyses, the required sample size increases to 2,780. After accounting for a combined rate of crossover and dropouts of 3% (as derived from the pilot phase), we will target a total sample size of 2,866.

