**STandard versus Accelerated initiation of Renal Replacement Therapy in Acute Kidney Injury
(STARRT-AKI): A Multi-Centre, Randomized, Controlled Trial**

**Statistical Analysis Plan
May 23, 2019
CONFIDENTIAL**

Principal Investigators:

[name] MSc FRCPC
Division of Critical Care Medicine, Faculty of Medicine and Dentistry
University of Alberta
Associate Professor, Division of Critical Care Medicine
University of Alberta
[name]
[name]
Edmonton, Alberta
[name]
[contact]
[contact]
Email: [contact]

[name], MDCM MPH FRCPC
Division of Nephrology, Department of Medicine
St. Michael's Hospital
Assistant Professor, Department of Medicine
University of Toronto
[name]
Toronto, Ontario
[name]
[contact]
[contact]
Email: [contact]

ClinicalTrials.gov Identifier: NCT02568722

Statistical analysis plan for the Standard versus Accelerated Initiation of Renal Replacement Therapy in Acute Kidney Injury (STARRT-AKI) trial

The optimal time for renal replacement therapy (RRT) initiation in critically ill patients with acute kidney injury (AKI) is uncertain and presents a dilemma for clinicians. ¹ Numerous observational studies that have described an association between the timing of RRT initiation and outcomes have been susceptible to bias and unmeasured confounding, ²⁻⁴ while recent randomised controlled trials ⁵⁻⁷ have disparate findings.

The Standard versus Accelerated Initiation of Renal Replacement Therapy in Acute Kidney Injury (STARRT-AKI) trial will be the largest trial to date to evaluate the timing of RRT initiation among critically ill patients with AKI. In this article we describe the pre-specified statistical analysis plan (SAP) for the STARRT-AKI trial finalised before the completion of targeted recruitment and locking of the trial database for analysis, in accordance with consensus recommendations.⁸

Trial design

The STARRT-AKI is a multinational, randomised, open-label, controlled trial of critically ill patients with severe AKI that is designed to compare the clinical and cost-effectiveness of a pre-emptive (accelerated) strategy of RRT initiation versus a strategy of watchful waiting and RRT initiation guided by AKI-related indications and clinician judgment (standard). ⁹ The protocol was finalised on 5 October 2015, without intervening amendments. ¹⁰

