The primary hypothesis is that a strategy of accelerated RRT initiation will reduce 90-day all-cause mortality, compared with a strategy of standard RRT initiation, among critically ill patients with severe AKI.

Trial sites

The STARRT-AKI trial will recruit a minimum of 2866 patients across an estimated 170 sites in 15 countries.

Patient population Adult critically ill patients with severe AKI are eligible for enrolment.

Inclusion criteria

All the inclusion criteria below must be fulfilled: ● age 18 years or over on the day of eligibility screening; ● admission to an intensive care unit (ICU); ● evidence of kidney dysfunction (serum creatinine, ≥ 1.00 g/mol/L for women and 1.30 g/mol/L for men, based on last blood work available before screening); and ● evidence of severe AKI based on at least one of the following three criteria.

- ▶ twofold increase in serum creatinine from baseline; or
- ▶ current serum creatinine is 354 g/mol/L or more, with a minimum increase of 27 μ mol/L from the baseline serum creatinine; or
- ▶ urine output is less than 6 ml/kg in the prior 12 hours.

Exclusion criteria

The exclusion criteria are the following (none may be present): ● potassium at time of screening greater than 5.5 mmol/L; ● bicarbonate at time of screening less than 15 mmol/L; ● presence of a drug overdose or dialysable toxin that necessitates RRT; ● lack of commitment to provide RRT as part of philosophy of care; ● receipt of any RRT in the preceding 2 months; ● kidney transplant within the past 365 days; ● known advanced chronic kidney disease (CKD), defined by estimated glomerular filtration rate (eGFR) of less than 20 mL/min/1.73 m²; ● presence or clinical suspicion of renal obstruction, rapidly progressive glomerulonephritis, vasculitis, thrombotic microangiopathy or acute interstitial nephritis; ● the clinicians caring for the patient believe that immediate RRT is mandated. After fulfilling the above inclusion/exclusion criteria, the study team will speak to

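### The final significance level of 0.044 is the boundary for 2,866 patients, and the SAP keeps it after recording an extension to at least 3,000

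*SAP*

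**What the plan says.** The SAP, under Analysis principles, states that "the overall type I error probability for the primary outcome will not exceed 5" per cent. It uses an O'Brien-Fleming stopping boundary with interim p thresholds of 0.00001473, 0.003045 and 0.0183, "and a required significance level of 0.044 at the final analysis". The reference given is the alpha spending function approach.

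The interims, under Interim analyses and the Data Safety Monitoring Board, are placed "following the completion of 90-day follow-up for the 716th, 1432nd and 2150th patient". Protocol section 2.10 describes the same looks as analyses that "will be done when 25, 50 and 75% of planned enrollees have completed 90-day follow-up", and in section 2.9 "we will target a total sample size of 2,866".

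The SAP's Sample size section then reports that after the third interim (24 April 2019) the DSMB "supported the extension of recruitment to achieve a sample size of a minimum of 3000 patients". The SAP is dated 23 May 2019, so it was written after that decision. Its Trial sites section still says "The STARRT-AKI trial will recruit a minimum of 2866 patients across an estimated 170 sites in 15 countries", and its Trial design section says "The protocol was finalised on 5 October 2015, without intervening amendments".

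Neither document recomputes the final level for 3,000 patients or gives a rule for a changed maximum sample size.

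**The concern.** A group-sequential boundary depends on where the looks fall as fractions of the final information. Once the final number rises, the interims already performed sit at smaller fractions than planned. The final statistic is then less correlated with the interim statistics. If the thresholds stay the same, the probability of crossing at least one of them under the null goes up.

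The value 0.044 decides the primary outcome, 90-day mortality. If it belongs to a sample size that the SAP no longer targets, the promise of at most 5% is not strictly kept, and a borderline result could be challenged on that ground.

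**Working it through.** **Inputs.** Two-sided tests, overall alpha 0.05, and thresholds 0.00001473, 0.003045, 0.0183 and 0.044 (SAP, Analysis principles). Looks at 716, 1,432 and 2,150 patients (SAP, Interim analyses). Total 2,866 (protocol 2.9) and at least 3,000 (SAP, Sample size). Information is taken as proportional to patients.

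**Step 1: reproduce the SAP's figures.** The Lan-DeMets O'Brien-Fleming-type function with 0.025 per side spends, over both sides, α(t) = 4[1 − Φ(2.2414/√t)], where 2.2414 is the upper 0.0125 normal quantile. Boundaries follow by recursive numerical integration.

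| t | cumulative alpha | z | nominal p |
|---|---|---|---|
| 0.25 | 0.00001473 | 4.333 | 0.00001473 |
| 0.50 | 0.00305 | 2.963 | 0.003045 |
| 0.75 | 0.01930 | 2.359 | 0.01832 |
| 1 | 0.05000 | 2.014 | 0.04400 |

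All four stated values are reproduced. The classical O'Brien-Fleming boundary does not match (0.0000515, 0.0042, 0.0194, 0.0429). Since 716, 1,432 and 2,150 are 25.0, 50.0 and 75.0% of 2,866, the value 0.044 is tied to 2,866.

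**Step 2: keep the stated thresholds and raise the final number.** At 3,000 the looks fall at 716/3,000 = 0.239, 1,432/3,000 = 0.477 and 2,150/3,000 = 0.717. The correlation between the third-look and final statistics falls from √(2,150/2,866) = 0.866 to √(2,150/3,000) = 0.847. The alpha spent by the third look is unchanged at 1.93%. The final step then adds 3.15% instead of 3.07%.

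| Final total | Overall alpha with 0.044 | Final level that gives 5% |
|---|---|---|
| 2,866 | 5.00% | 0.0440 (z = 2.014) |
| 3,000 | 5.07% | 0.0432 (z = 2.022) |
| 3,100 (assumed, as 3,000 is a minimum) | 5.13% | 0.0426 (z = 2.028) |

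**Step 3: the alternative route.** Rebuilding all four boundaries at the 3,000-patient fractions gives a final level of 0.0449, but with interim thresholds of 0.00000895, 0.00235 and 0.0155, which are not those in the SAP. Neither route gives 0.044 at 3,000.

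**Step 4: if the extension depended on the data.** Suppose the choice between 2,866 and 3,000 was made after seeing the third-look statistic. Taking the smaller or the larger conditional error at every value of that statistic bounds the overall alpha between 4.92% and 5.16%.

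**Step 5: practical size.** At 1,500 per arm and 40% mortality, the critical difference in deaths is z × √(2 × 0.4 × 0.6 × 1,500) = 26.83z, which is 54.04 at 0.044 and 54.26 at 0.0432. The chance that a final p falls between the two levels (single final look) is about 0.1% under the null, 0.3% at a 3-point difference and 0.1% at the planned 6 points. Power at 3,000 for 40% against 34%, with all four looks, is 92.2% at 0.044 and 92.1% at 0.0432.

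**The case against.** The strongest objection is that the excess is smaller than the uncertainty in the calculation.

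- **Look sizes.** The SAP gives triggers for the interims, not the numbers analysed. If the third look contained 2,250 patients, overall alpha at 3,000 would be 5.01%; with 2,300 it would be 4.98%. If 3% are lost from the final 3,000 (leaving 2,910) while the interim counts are completers, it would be 5.02%.
- **Stratification.** Randomisation is stratified by site, but the primary comparison is unadjusted. If sites differ in mortality, the test is somewhat conservative. A reduction of about 0.6% in the variance of the test statistic would remove the excess. The documents give no between-site correlation from which to judge this.
- **Whole deaths.** With 1,500 per arm and 1,200 deaths in total, the difference in deaths must be even, and both levels require 56.
- **Sample size wording.** A total of 3,000 satisfies a minimum of 2,866, so the Trial sites sentence is out of date rather than contradictory.
- **Other documents.** The DSMB charter is cited but is not among the documents reviewed, so a recomputation there cannot be excluded.

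These points stand as limits on size and certainty. They do not make 0.044 the right level for the look schedule that the SAP itself states. A nominal level should be set from that schedule, not left to be offset by possible conservatism elsewhere. The charter could settle the matter, but the SAP, written after the extension, still prints the 2,866-patient value.

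**Conclusion.** The concern holds and is minor. The stated final level is the 2,866-patient boundary. Under the SAP's own look schedule and a final total of 3,000, it gives about 5.07% instead of at most 5%, and about 0.0432 is needed.

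This rests on information proportional to patients, looks at exactly 716, 1,432 and 2,150, and an extension made independently of the treatment effect. If the extension depended on the third-look result, the overall error lies between 4.92% and 5.16%, so an excess is not certain under every rule. The SAP does not say which case applies, and the DSMB that supported the extension reviews unblinded outcomes. The conclusion on the primary outcome changes only for a final p between about 0.0432 and 0.0440.

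**What to change.** Before database lock:

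1. Replace 0.044 with a final level recomputed from the three interim thresholds already used, the numbers at those looks and the actual final total. With looks at 716, 1,432 and 2,150 this is about 0.0432 at 3,000 or 0.0426 at 3,100.
2. State one final sample size in both the Trial sites and the Sample size sections.
3. Add a sentence saying whether the extension was decided without regard to the treatment effect, because the recomputed level holds 5% only in that case.

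The cost is one boundary calculation, two or three sentences and about 0.1 percentage point of power.
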